2 OBJECTIVES AND HYPOTHESES

2.1 Objectives

Primary Objective

To evaluate the long-term safety of sirukumab in subjects with RA, who are refractory to disease modifying antirheumatic drugs (DMARD) or anti-TNF α agents.

Secondary Objectives

The secondary objectives are to observe the following long-term effects of sirukumab in subjects with RA who are refractory to DMARDs or anti-TNF α agents on:

- Efficacy
- Pharmacokinetics
- Immunogenicity
- Pharmacodynamics

CNTO 136 (sirukumab): Clinical Protocol CNTO136ARA3004 – Amendment 3

- Pharmacogenetics
- PFS-AI usability (as defined in a separate substudy protocol)

2.2 Hypothesis

No formal hypothesis is being tested.

3 STUDY DESIGN AND RATIONALE

3.1 Overview of Study Design

Subjects will become eligible to participate in this LTE study when they have completed participation in studies CNTO136ARA3002 (104 weeks) or CNTO136ARA3003 (52 weeks). The purpose of this LTE study is to evaluate the safety, efficacy, and pharmacologic effects of sirukumab for a minimum duration of 1 to 4 additional years and a maximum total duration of approximately 5 years across the combined protocols (CNTO136ARA3002 (2 years) or CNTO136ARA3003 (1 year) + CNTO136ARA3004 (1 to 4 years) = maximum of 5 years treatment).

The SmartJect™ Autoinjector (PFS-AI) is expected to be used by the majority of subjects in study CNTO136ARA3004. In the event PFS-AIs are unavailable at the time of a subject's enrollment in this protocol, sirukumab PFS-UltrSAFE (PFS-U), the same device used in the CNTO136ARA3002 and CNTO136ARA3003 studies, will be provided until such time as the PFS-AIs become available. Upon availability of PFS-AI trial supplies, subjects who are newly entering the CNTO136ARA3004 protocol will be trained on the operation of PFS-AI and perform self-administration of study agent using PFS-AI at the Week 2 study visit and return to the study site at Week 4 for self-administration with PFS-AI. In the event PFS-AIs are unavailable at the time of a subject's enrollment in this protocol, training on the use of a PFS-AI will be provided at the next study visit when the PFS-AI is available.

During the Week 104 visit in CNTO136ARA3002 or the Week 52 visit in CNTO136ARA3003, subjects will sign the informed consent form (ICF) to enter study CNTO136ARA3004. As a result, the Week 104 visit in study CNTO136ARA3002 and the Week 52 visit in study CNTO136ARA3003 will correspond to the Week 0 visit in the CNTO136ARA3004 study.

After a minimum of 1 year treatment in CNTO136ARA3004 for subjects from study CNTO136ARA3002, or a minimum of 2 years of treatment in CNTO136ARA3004 for subjects from CNTO136ARA3003, and after sirukumab is approved for the treatment of RA in the subject's country of residence, the Sponsor may no longer offer study treatment in CNTO136ARA3004 for those specific subjects. At that point the subject will have the opportunity to discuss treatment options with their treating physician.

The maximum duration of participation in this study is 208 weeks, followed by approximately 16 weeks of safety and efficacy follow-up after the administration of the final study agent injection of sirukumab. Only 1 database lock (DBL; at the end of the study) is planned. Additional data releases or locks may occur as needed. The study will end with the last visit for the last subject participating in the study.

CNTO 136 (sirukumab): Clinical Protocol CNTO136ARA3004 – Amendment 3

Study treatment will remain blinded in CNTO136ARA3004 until the following 3 conditions have been met: the Week 52 DBL occurs in study CNTO136ARA3002, the Week 24 DBL occurs in study CNTO136ARA3003, and the last AI usability substudy subject completes the Week 16 visit or terminates from the study. Thereafter study CNTO136ARA3004 will become open-label and placebo injections will be discontinued in the SC sirukumab 50 mg treatment group. Once study CNTO136ARA3004 becomes open-label, study subjects will receive open-label study agent through IVRS/IWRS. However, when this study becomes open-label, any subjects who still remain in studies CNTO136ARA3002 and CNTO136ARA3003 due to staggered enrollment will continue to receive blinded treatment until they complete participation in those studies.

Protocol waivers or exemptions are not allowed with the exception of immediate safety concerns. Therefore, adherence to the study design requirements, including those specified in the Time and Events Schedules are essential and required for study conduct.

Subject safety will be monitored through the end of the study as delineated in the Time and Events Schedules.

The primary endpoint is the number of subjects with each of the following long-term safety events through the end of the study: cardiovascular (CV) SAEs, malignancies, serious infections, and gastrointestinal perforations.

The major secondary endpoint is laboratory parameters of interest (neutrophils, platelets, hepatobiliary parameters, and lipid parameters).

Serum samples will be collected for the evaluation of sirukumab PK and antibodies to sirukumab. Other samples to be collected include serum and whole blood RNA for the evaluation of inflammation-associated proteins and other analytes. These samples will be used to better understand the biology of RA, to analyze differences between responders and non-responders, and to assess loss of response.

A pharmacogenetics blood sample to assess genetic factors such as DNA methylation patterns will be collected from subjects who consent separately to the pharmacogenetics component of the study where local regulations permit. Participation in the pharmacogenetics research component of this study is optional.

Health economics data including subject employability, daily work productivity, and reduced time lost from work will be collected.

Safety and tolerability will be assessed by monitoring AEs, clinical laboratory tests, vital signs, physical examinations, and concomitant medication review.

[figure not shown]
An independent Clinical Events Committee (CEC) will be established for this study to review case information on serious cardiovascular (CV) events (myocardial infarction, stroke, death, hospitalization for angina, hospitalization for transient ischemic attack (TIA); see Section 11.11).

CNTO 136 (sirukumab): Clinical Protocol CNTO136ARA3004 – Amendment 3

An independent Data Monitoring Committee (DMC) will be commissioned for this study to review unblinded data periodically for the blinded portion of the study and whenever deemed necessary to monitor subject safety (see Section 11.10).

All assessments will be performed according to the Time and Events Schedules. A diagram of the study design is provided below (Figure 1).

Figure 1: CNTO136ARA3004 Study Design and Study Timeline

3.2 Study Design Rationale

This study is designed to examine the long-term safety and efficacy of sirukumab, the effects of sirukumab on physical function, pharmacokinetics, and immunogenicity of sirukumab in subjects with moderately to severely active RA who are refractory or intolerant to DMARDs or anti-TNF α therapy.

CNTO 136 (sirukumab): Clinical Protocol CNTO136ARA3004 – Amendment 3

Additionally, this study is designed to obtain experience in the use of the SmartJect™ Autoinjector (PFS-AI) in all subjects enrolled in CNTO136ARA3004. More data regarding the usability of the autoinjector will be evaluated in the PFS-AI substudy. Additional details are provided in Section 9.6.

3.2.1 Study Population

Subjects who complete the Week 104 (CNTO136ARA3002) visit and study agent administration or the Week 52 (CNTO136ARA3003) visit and study agent administration will be deemed to have completed participation in those studies and will be eligible to enroll in this long-term extension study.

3.2.2 Treatment Groups, Dosage, and Dose Administration Interval

Subjects will continue to receive the same dosing regimen they received at the Week 104 (CNTO136ARA3002) and at Week 52 visit (CNTO136ARA3003) in blinded fashion until the following 3 conditions have been met: the Week 52 DBL occurs in study CNTO136ARA3002, the Week 24 DBL occurs in study CNTO136ARA3003, and the last AI usability substudy subject completes the Week 16 visit or terminates from the study. Thereafter the same treatment assignment will be continued, but the study will no longer be blinded and will become open-label.

The 2 sirukumab doses to be administered in this study are as follows:

- 100 mg q2 weeks
- 50 mg q4 weeks

Following the database lock for the primary endpoint, analysis of CNTO136ARA3002 and CNTO136ARA3003 PK and efficacy data showed that there was no clear dose response between the sirukumab SC 50 mg q4 weeks and sirukumab SC 100 mg q2 weeks dose groups across efficacy endpoints. Furthermore, there were a greater proportion of subjects with hypersensitivity reactions and injection site reactions in the sirukumab 100 mg q2 weeks dose group compared with the sirukumab 50 mg q4 weeks dose group. Therefore, to allow for minimization of the exposure to this immunosuppressant biologic agent, subjects treated with SC sirukumab 100 mg q2 weeks will be offered the option to reduce the sirukumab dose to 50 mg q4 weeks at the investigator's discretion after the study becomes open-label. This decision can be made at the subject's first or second major resupply visit (up until approximately 7 months) after implementation of Amendment 3 at the study site.

3.2.3 Study Phases and Duration of Treatment

There will be 3 phases of this LTE study: Blinded active treatment, open-label treatment, and safety and efficacy follow-up.

CNTO 136 (sirukumab): Clinical Protocol CNTO136ARA3004 – Amendment 3

As described in Section 3.2.2, the blinded active treatment phase will continue until following 3 conditions have been met: the Week 52 DBL occurs in study CNTO136ARA3002, the Week 24 DBL occurs in study CNTO136ARA3003, and the last AI usability substudy subject completes the Week 16 visit or terminates from the study.

The open-label treatment phase of the study will begin after those 3 conditions have been met, and will continue through the last scheduled dose for all subjects. The safety and efficacy follow-up will include approximately 16 weeks of study evaluations following the last administration of study agent, including follow-up for patients who discontinued study treatment prior to their last scheduled dose. The safety and efficacy follow-up allows for monitoring of the subject for a period of equivalent to at least 5 times the half-life of sirukumab.

The maximum duration of the study is expected to be 156 weeks for subjects enrolling after participation in study CNTO136ARA3002 and 208 weeks for subjects enrolling after participation in study CNTO136ARA3003, followed by approximately 16 weeks of safety and efficacy follow-up after the administration of the final study agent injection of sirukumab.

After a minimum of 1 year treatment in CNTO136ARA3004 for subjects from study CNTO136ARA3002, or a minimum of 2 years of treatment in CNTO136ARA3004 for subjects from CNTO136ARA3003, and after sirukumab is approved for the treatment of RA in the subject's country of residence, the Sponsor may no longer offer study treatment in CNTO136ARA3004 for those specific subjects. At that point the subject will have the opportunity to discuss treatment options with their treating physician.

3.2.4 Study Control, Randomization, and Blinding

Blinded matching placebo injections will be used to reduce potential bias during data collection and evaluation of clinical endpoints and will be maintained until the following 3 conditions have been met: the Week 52 DBL occurs in study CNTO136ARA3002, the Week 24 DBL occurs in study CNTO136ARA3003, and the last AI usability substudy subject completes the Week 16 visit or terminates from the study. Thereafter the CNTO136ARA3004 study will become open-label.

3.2.5 Efficacy Evaluations

The efficacy evaluations chosen for this study are consistent with those in primary studies CNTO136ARA3002 and CNTO136ARA3003.

RA response evaluations include:

- American College of Rheumatology (ACR) responses
- Disease Activity Index Score 28 (DAS28)
- Health Assessment Questionnaire-Disability Index (HAQ-DI)
- ACR/The European League Against Rheumatism (EULAR) remission

CNTO 136 (sirukumab): Clinical Protocol CNTO136ARA3004 – Amendment 3

Patient Reported Outcome (PRO) evaluations include:

- 36-Item Short Form (SF-36)
- Work Limitations Questionnaire (WLQ)
- Health Economics Questionnaire (HECONQ)

The medical resource usage and health economics evaluations chosen for this study have also been used in studies CNTO136ARA3002 and CNTO136ARA3003.

3.2.6 Safety Evaluations

Based upon the emerging safety profile of other anti-IL-6 agents, as well as the sirukumab safety data to date, several AE of interest have been identified and will be monitored and assessed in this study. These are: hematologic laboratory abnormalities (decreases in neutrophils and platelets), hepatobiliary laboratory abnormalities, lipid parameter abnormalities, serious CV events, infections, malignancies, and gastrointestinal perforations.¹

Subject safety evaluations including the reporting of AEs, clinical laboratory tests (hematology, serum chemistry, and lipid panels), pregnancy tests, and vital signs (blood pressure and body weight) etc. will be monitored through the end of the study as delineated in the Time and Events Schedules. In addition, an independent DMC will review unblinded data periodically for the blinded portion of the study and whenever deemed necessary to monitor subject safety.

Laboratory parameter abnormalities:

IL-6 is a pleiotropic cytokine necessary for hematopoiesis and IL-6 inhibition has been shown to cause a reduction in both neutrophils and platelets. In addition, IL-6 inhibition has been associated with reversible elevation in liver enzymes. Mechanisms by which this might occur include inhibition of the hepatoprotective effect of IL-6, leaving hepatocytes susceptible to effects of toxins and other stresses. Lipid abnormalities have also been observed, both in the sirukumab Phase 2 study C1377T04, as well as with other anti-IL-6 agents. The mechanism by which this occurs is not fully understood.

Cardiovascular events:

Patients with RA are known to have an increased risk of serious CV events compared with the general population. In addition, in the sirukumab clinical programs, significant changes in lipid laboratory parameters have been observed, as with other agents that block IL-6. The clinical significance of these changes is not known. Nonetheless, serious CV events are considered AEs of interest and will be closely monitored in the sirukumab program. In order to fully understand CV events in this study, Major Adverse Cardiovascular Events (MACE), defined as myocardial infarction, stroke, death, hospitalization for unstable angina, and hospitalization for TIA, will be collected and prospectively adjudicated by an external CEC. The CEC is an independent committee composed of external specialists, blinded to treatment assignment, who will be commissioned to review case information on serious CV events (myocardial infarction, stroke,

death, hospitalization for angina, hospitalization for TIA). The operations, processes, and definitions to be employed by the committee will be defined in the CEC charter. This will allow external review of cases and determination of diagnosis prior to analysis. See Section 11.11 for a complete discussion of the CEC.

Other events of interest:

Sirukumab, by its mechanism of action as an IL-6 inhibitor, would be expected to have some properties of immunosuppression. As such, increased susceptibility to certain infections is a potential risk. IL-6 deficient mice have been found to be susceptible to infections with *Listeria monocytogenes*, *Toxoplasma gondii*, and *Candida albicans*.^{6,38,44} In addition, as an IL-6 inhibitor, sirukumab may have some effect on the risk of malignancy by affecting immune surveillance, particularly in a subject population (RA) already at increased risk for the development of lymphoma and leukemia. Further, gastrointestinal perforations have been reported with another anti-IL-6 agent at rates higher than the rate found in RA subjects.¹

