In this substudy, a select number of subjects at selected sites in English-speaking countries who are enrolled in CNTO136ARA3004 will be consented and enrolled in a SmartJect™ AI Usability substudy. Site personnel in this substudy will observe and document 2 scheduled self-administrations of study agent by subjects using the PFS-AI. All substudy subjects will also complete an e-diary regarding their experiences with at-home use of PFS-AI.

STATISTICAL METHODS

Statistical analysis will be done by the Sponsor or under the authority of the Sponsor.

Subjects will continue to receive the same treatment regimen administered in studies CNTO136ARA3002 and CNTO136ARA3003 at Weeks 104 and 52, respectively:

- Group 1: Sirukumab 100 mg SC q2 weeks
- Group 2: Sirukumab 50 mg SC q4 weeks

After the study becomes open-label, subjects in Group 1 will be offered the option (at the discretion of the investigator) to reduce the sirukumab dose to 50 mg q4 weeks for the remainder of the trial.

Since the treatment groups are not randomly assigned in this study, no formal hypothesis testing is planned. The efficacy, safety, and PK/PD/immunogenicity analyses will be performed separately for subjects who complete studies CNTO136ARA3002 and CNTO136ARA3003. The analyses will include all subjects enrolled by study and by treatment group above.

Only 1 DBL (at the end of the study) is planned. Safety, efficacy, and PK/PD/immunogenicity assessments will be analyzed for subjects enrolled in the CNTO136ARA3004 by previous study and by treatment group.

CNTO 136 (sirukumab): Clinical Protocol CNTO136ARA3004 – Amendment 3

Additional data releases or locks may occur as needed. The analyses based on these data releases or locks intend to integrate data from CNTO136ARA3002 and CNTO136ARA3003 with this study for the long-term PK, immunogenicity, safety and efficacy data of all subjects enrolled in these studies. A separate SAP for integration will be developed to specify the analyses and data handling rules.

- **Sample Size Determination**

All eligible subjects will be included in this LTE study. No power calculations were performed as there is no statistical hypothesis testing planned.

- **Interim Analysis**

No formal interim analyses are planned, though analyses based on interim releases and locks may be carried out for integrated PK, immunogenicity, safety and efficacy data.

- **Primary Analyses**

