5 TREATMENT ALLOCATION AND BLINDING

5.1 Treatment Allocation

There will be 2 treatment groups for the duration of this study:

Group 1: Sirukumab 100 mg q2 weeks through Week 156 for subjects who enrolled after completing participation in CNTO136ARA3002 and through Week 208 for subjects who enrolled after completing participation in CNTO136ARA3003.

Group 2: Sirukumab 50 mg q4 weeks through Week 156 for subjects who enrolled after completing participation in CNTO136ARA3002 and through Week 208 for subjects who enrolled after completing participation in CNTO136ARA3003.

After the study becomes open-label, subjects treated with SC sirukumab 100 mg q2 weeks will be offered the option to reduce the sirukumab dose to 50 mg q4 weeks at the investigator's discretion. This decision can be made at the subject's first or second major resupply visit (up until approximately 7 months) after implementation of Amendment 3 at the study site.

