11 STATISTICAL METHODS

Statistical analysis will be done by the Sponsor or under the authority of the Sponsor. Descriptive statistics (eg, mean, median, standard deviation, interquartile range, minimum, and maximum) will be used to summarize continuous variables. Counts and percentages will be used to summarize categorical variables.

Subjects will continue to receive the same treatment regimen administered in studies CNTO136ARA3002 and CNTO136ARA3003 at Weeks 104 and 52, respectively:

- Group 1: Sirukumab 100 mg SC q2 weeks
- Group 2: Sirukumab 50 mg SC q4 weeks

CNTO 136 (sirukumab): Clinical Protocol CNTO136ARA3004 – Amendment 3

After the study becomes open-label, subjects treated with SC sirukumab 100 mg q2 weeks will be offered the option to reduce the sirukumab dose to 50 mg q4 weeks at the investigator's discretion. This decision can be made at the subject's first or second major resupply visit (up until approximately 7 months) after implementation of Amendment 3 at the study site.

Since the treatment groups are not randomly assigned in this study, no formal hypothesis testing is planned. The efficacy, safety, and PK/PD/immunogenicity analyses will be performed separately for subjects who complete studies CNTO136ARA3002 and CNTO136ARA3003. The analyses will include all subjects enrolled by study and by treatment group above.

Additional data releases or locks may occur periodically as needed. The analyses based on these data releases or locks intend to integrate data from CNTO136ARA3002 and CNTO136ARA3003 with this study for the long-term PK, immunogenicity, safety and efficacy data of all subjects enrolled in these studies. A separate SAP for integration will be developed to specify the analyses and data handling rules.

An independent DMC will monitor the safety of the blinded portion of the study in unblinded fashion on a regular basis and whenever deemed necessary. Additional details are provided in Section 11.10.

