11.2.1 Primary Endpoint

The number of subjects with each of the following long-term safety events through the end of study: cardiovascular SAEs, malignancies, serious infections, and gastrointestinal perforations will be summarized.

Serious cardiovascular events adjudicated by the CEC will be summarized by treatment group.

No hypothesis testing will be performed.

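### The primary safety analysis gives cumulative counts and percentages with no person-time, exposure interval or reference rate, so it cannot show whether risk changes with exposure or exceeds the RA background

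*Protocol*

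**What the plan says.** The primary objective (Protocol 2.1) is "To evaluate the long-term safety of sirukumab in subjects with RA" refractory to DMARDs or anti-TNFα agents. Section 2.2 states that no formal hypothesis is tested.

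Section 3.2.6 explains why certain events are followed closely. On malignancy it says that "sirukumab may have some effect on the risk of malignancy by affecting immune surveillance, particularly in a subject population (RA) already at increased risk" for lymphoma and leukemia. On perforation it says that "gastrointestinal perforations have been reported with another anti-IL-6 agent at rates higher than the rate found in RA subjects". It gives no background rate for either.

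The primary analysis (11.2.1) states that the numbers of subjects with "cardiovascular SAEs, malignancies, serious infections, and gastrointestinal perforations will be summarized", cumulatively to study end. CEC-adjudicated cardiovascular events are shown by treatment group. Section 11 adds percentages for categorical variables and separate analysis by parent study and treatment group. Section 11.8 adds breakdowns of cardiovascular SAEs and malignancies by type.

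On design, Section 5.1 says "There will be 2 treatment groups for the duration of this study", and both groups receive sirukumab. Section 11 says "Since the treatment groups are not randomly assigned in this study, no formal hypothesis testing is planned". The synopsis gives no enrolment figure: "All eligible subjects will be included in this LTE study", and "No power calculations were performed as there is no statistical hypothesis testing planned".

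**The concern.** An extension study exists largely to learn what happens with longer exposure. The four primary event types are nevertheless the data with no planned time dimension: laboratory toxicity grades (11.2.2) and efficacy endpoints (11.2.3) are summarised over time, and the primary events are not.

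Follow-up is also unequal. Section 3.2.3 allows up to 156 weeks of treatment from CNTO136ARA3002 and 208 from CNTO136ARA3003. Supply may stop after 1 or 2 years, respectively, once the drug is approved in a subject's country. A percentage of subjects with an event therefore mixes the event rate with the length of observation.

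No arm is untreated. A comparison of the two dose groups cannot reveal a risk common to both, and it is further blurred because 100 mg subjects may move to 50 mg after the study opens its label. The reader of the final table would have the counts but no means of judging whether they are high for an RA population, or whether they accumulate faster late than early.

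**Working it through.** The plan states no event rate, enrolment or precision target, so there is no figure to reproduce. The calculations below are illustrations. All subject numbers, counts and rates in them are assumptions; only the durations come from the protocol.

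**1. Effect of exposure on a crude percentage.** With constant rate λ, the percentage with an event by time t is 100 × (1 − exp(−λt)). Take λ = 0.01 per year (1.0 per 100 subject-years):

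| Years | Crude % |
|---|---|
| 1 | 1.00 |
| 2 | 1.98 |
| 3 (156 weeks) | 2.96 |
| 4 (208 weeks) | 3.92 |

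Year 4 against year 1 is a 3.94-fold ratio; the two maximum durations differ 1.33-fold (3.92/2.96). Because analyses are separate by parent study, the 1.33-fold gap matters when the two sets of results are compared. Variation from early stopping remains within each set.

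**2. The same count under different exposure.** Ten affected subjects among 1,000 is 1.0% in every row. The rate is 10/person-years, and the exact limits are ½χ²(0.025; 20) and ½χ²(0.975; 22), divided by person-years:

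| Mean years | Rate per 100 subject-years (95% CI) |
|---|---|
| 1 | 1.00 (0.48–1.84) |
| 2 | 0.50 (0.24–0.92) |
| 3 | 0.33 (0.16–0.61) |
| 4 | 0.25 (0.12–0.46) |

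**3. Time pattern.** Suppose 1,000 subjects are followed for three years, giving about 1,000 subject-years in year 1 and 2,000 in years 2–3. Eight events then two give 0.8 and 0.1 per 100 subject-years; two then eight give 0.2 and 0.4. Both produce ten subjects in the planned table.

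**4. Reference.** Ten events in 2,000 subject-years, set against an assumed background of 0.25, 0.5 or 1.0 per 100 (5, 10 or 20 expected), give observed/expected ratios of 2.0, 1.0 or 0.5.

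**5. What a reference could and could not deliver.** Assume 1,000–2,000 subjects followed 2–2.5 years, so 1,000 × 2 = 2,000 to 2,000 × 2.5 = 5,000 subject-years.

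- Malignancy at 0.5–1.0 per 100 subject-years: 10–50 expected. If observed equals expected, the ratio's 95% interval is 0.48–1.84 (10) or 0.74–1.32 (50). With 12 observed against 10 expected, the upper limit is 20.96/10 = 2.10.
- Perforation at 0.1 per 100 subject-years: 2–5 expected. If observed equals expected, the upper limits are 3.61 and 2.33.
- Power of an exact one-sided 0.025 Poisson test to detect a doubling, over 500 to 6,000 subject-years: 42% to over 99% at a reference of 1.0 per 100 subject-years, but 8% to 54% at 0.1.

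**6. Exposure intervals.** Week 0 of this study is Week 104 or Week 52 of the parent study (3.1). A subject treated with sirukumab since parent baseline enters observation here in the third or second 52-week interval after first dose. Total treatment can reach 104 + 156 = 260 or 52 + 208 = 260 weeks. Data from this study alone therefore cover the later intervals, with delayed entry; the earlier ones need parent-study data.

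**The case against.** The strongest reply is that the objective is descriptive. No hypothesis is tested, and frequencies by parent study and dose group, with type breakdowns and adjudicated cardiovascular events, do describe long-term safety. That stands. A reader might infer that the long-term safety question cannot be answered at all, or that the plan offers nothing beyond a raw count. The documents support neither: Section 11 provides percentages and group summaries, and Section 11.8 provides breakdowns by type.

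Section 3.2.6 is also rationale, not a commitment to a comparison. Only perforation is set explicitly against an RA rate, and that for another agent; for malignancy the comparison is implied. This stands too, and limits the point to a gap between the reason given for following these events and what the analysis can show.

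The missing elements may be elsewhere. The SAP text was not available, and Section 11 assigns integrated long-term safety analyses to a separate SAP. Absence is therefore asserted for the protocol only. The protocol does not say that the integration SAP changes this study's own primary analysis.

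Finally, external comparators are weak here. RA itself raises lymphoma risk, which would push a ratio against the general population above 1 without any drug effect. Entry is limited to parent-study completers (4.1, 4.2), which could push it down. This is a good reason to treat such a ratio as context only. It does not touch the case for person-time and exposure intervals.

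**Conclusion.** The point holds for the protocol as written. The primary output describes how many subjects were affected, but it cannot show whether risk changes with longer exposure or exceeds the RA background. Under an assumed constant rate of 1.0 per 100 subject-years, exposure alone moves the crude percentage 3.94-fold between one and four years. Opposite time patterns can give the same count.

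A reader might also infer that adding a reference rate would exclude a doubling of risk. That does not follow. It fails with 12 malignancies against 10 expected (upper limit 2.10), and with 2–5 expected perforations even when observed equals expected (3.61 and 2.33). Lymphoma alone, or a split by parent study, would be less precise than all malignancies together. The gain is interpretability, with honest intervals, and not a decisive test.

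This is a worthwhile improvement to the analysis, not a defect that invalidates the study. The numerical illustrations rest on assumed enrolment, follow-up and rates; the structural conclusion does not.

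**What to change.** Amend Section 11.2.1, or cite the SAP section that already does this:

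1. For each of the four event types, report incidence per 100 subject-years with exact Poisson 95% CI, by parent study and by dose actually received. State the rule for attributing events and person-time after a switch from 100 mg to 50 mg.
2. Show each event type by 52-week interval since first sirukumab dose, with subjects at risk and person-time in each interval. Subjects enter the risk set at their Week 0 in this study unless parent-study data are pooled under the integration SAP.
3. Before the final lock, name the external reference and label it supportive: published RA-cohort rates for malignancy, perforation, serious infection and cardiovascular events, plus a general-population standardised incidence ratio for malignancies excluding nonmelanoma skin cancer. State beside it that RA raises lymphoma risk, that only parent-study completers enter, and that follow-up ends about 16 weeks after the last dose.

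The cost is modest analysis work, with no added visits or procedures. Baselines are already taken from the parent studies (11.2), so linkage to them is planned. The downside is an imperfect external comparator. Fixing it in advance prevents its being chosen after the counts are known, which matters in a study that becomes open-label and allows data releases as needed.
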